Appendix 3F: Insurance

LEO Pharma has taken out relevant insurances covering the subjects in the present clinical trial in accordance with applicable laws and regulations.

Appendix 3G: Financial disclosure

Investigators will provide LEO Pharma with sufficient, accurate financial information as requested to allow LEO Pharma to submit complete and accurate financial certification or disclosure statements to the appropriate regulatory authorities. Investigators are responsible for providing information on financial interests during the course of the clinical trial and for 1 year after completion of the clinical trial, or for a longer period of time if required by local legislation.

Appendix 3H: Trial and site closure

Premature termination of trial or trial site

LEO Pharma, the investigator, the IRB/IECs or competent authorities may decide to stop the clinical trial, part of the trial or a trial site at any time, but agreement on procedures to be followed must be obtained.

If a clinical trial is suspended or prematurely terminated, the investigator must inform the subjects promptly and ensure appropriate therapy and follow-up. As specified by applicable regulatory requirements, the investigator or LEO Pharma must promptly inform IRB/IECs and provide a detailed written explanation. Relevant competent authorities must be informed.

The trial must be terminated if the perception of the benefit/risk ratio (judged from clinical signs and symptoms, (S)AEs and/or remarkable safety laboratory changes) becomes unfavourable for the continuation of the trial.

Reasons for the early closure of a trial site by LEO Pharma or investigator may include but are not limited to:

- Failure of the investigator to comply with the protocol, the requirements of the IRB/IEC or local health authorities, LEO Pharma procedures, or GCP guidelines.
- Inadequate recruitment of subjects by the investigator.

Completion of trial

Investigators will be informed when subject recruitment is to cease. Screening activities will be stopped at a trial site when the total requested number of subjects for the clinical trial has been obtained, irrespective of the specific site's planned inclusion number.

Trial sites will be closed upon trial completion. LEO Pharma will undertake arrangements for the collection and disposal of any unused trial material that the investigator is not required to

Trial ID: LP0162-1337 Date: 21-Feb-2022 Version: 14.0
Page 131 of 187

keep in his/her files. A trial site is considered closed when all required documents and trial supplies have been collected and a trial site closure visit has been performed.

Appendix 3I: Responsibilities

The signatory investigator is responsible for the approval of the clinical trial protocol and the CTR on behalf of all clinical trial investigators and as agreed to in a Signatory Investigator Agreement.

The national coordinating investigators are responsible for national issues relating to the clinical trial as agreed to in a National Coordinating Investigator Agreement.

Each participating investigator is responsible for all aspects of the clinical trial conduct at his/her trial site as agreed to in a Clinical Trial Agreement.

Appendix 3J: Country-specific end of treatment date

Subjects from the parent trial LP0162-1334, who consented to participate in the trial after May 2021, will end treatment by end of May 2022 in all countries.

Subjects from the parent trials LP0162-1325, -1326, -1339, -1341, -1342,-1343, -1346, and TRA-WEI-0015-I, who consented to participate in the trial after May 2021, will have a country-specific end of treatment date (Panel 17).

Panel 17: Country-specific last subject last treatment for parent trials LP0162-1325, -1326, -1339, -1341, -1342, -1343, -1346, and TRA-WEI-0015-I

Country	Approximate last treatment date in the trial*
US	May 2022
Germany	Aug 2021
UK	Sep 2022
France	Aug 2022
Italy	Jan 2023
Belgium	Nov 2022
Canada	May 2023
Spain	Jan 2023
Poland	May 2024
Czech Republic	Oct 2022
Japan	May 2023

^{*}These dates are estimates of availability of tralokinumab in the countries and could change.

Version: 14.0

Appendix 3K: COVID-19

Rationale

The current COVID-19 pandemic warrants many subjects in the ECZTEND trial to stay at home to comply with authority-issued preventive measures. This impacts subjects' ability to attend site visits in person. To follow authorities' restrictions and to safeguard the subjects in the ECZTEND trial as well as providing continued therapy to secure the scientific integrity, this clinical trial protocol appendix is installed to provide an opportunity for telephone visits and courier delivery of IMP and pregnancy tests to subjects in replacement of the site visits. In addition, inclusion criterion 2 is changed during COVID-19 restrictions, to allow subjects who are not able to attend all protocol-mandated visits of their parent trials due to COVID-19 to participate in trial LP0162-1337, if considered eligible for continued treatment by the investigator.

Subject eligibility

Inclusion criterion 2 in trial LP0162-1337 states:

- Subjects must have completed* the treatment period(s) of one of the parent trials:
 LP0162-1325, -1326, -1334, -1339, -1341, -1342, -1343, -1346, or TRA-WEI-0015-I.
 - * To be assessed on the first day of IMP administration (baseline).
- In trial LP0162-1334, a subject is considered to have completed the treatment period, if the subject has attended the Week 52 visit on site.
- In trials LP0162-1343 and TRA-WEI-0015-I, a subject is considered to have completed the treatment period, if the subject has attended the Week 16 visit on site.
- Change to inclusion criterion 2 in trial LP0162-1337 during COVID-19 restrictions:

 The change to inclusion criterion 2 described in the following only applies to subjects coming

from parent trials LP0162-1334, -1343, and TRA-WEI-0015-I, as these are the only parent trials ongoing at the time of this appendix.

For subjects who are not able to attend the above-mentioned visits at site in their parent trials due to COVID-19, inclusion criterion 2 is considered fulfilled if AEs have been collected over the telephone and if the investigator has evaluated and documented that the subject is considered to benefit from continued treatment in trial LP0162-1337, despite the missed visit(s) in the parent trial.

Page 133 of 187

Version: 14.0

eCRF recording

It must be recorded in the eCRF if a site visit was converted to a telephone visit (not applicable for the scheduled mandatory telephone visits in protocol version 13). This should be done in the comments log for each visit. 'Visit date' must also be documented.

If the subject is reached by telephone, use of emollients, AEs, concomitant medication and pregnancy test result (if applicable) must be collected. All other assessments should be marked 'Not done' in the eCRF, except for EASI, SCORAD, IGA, and weight, which should be left blank. The log line 'If not done, specify reason' in the assessment form must be answered with 'COVID-19' as well as the specific reason related to COVID-19, e.g. subject cannot visit site due to COVID-19 quarantine, or site is closed due to COVID-19.

In addition, the specific COVID-19-related reason for missing visit or performing visit as telephone visit must be entered in the 'Comments log' in the eCRF on subject level.

If no contact can be established between site and subject at a given visit, this must be recorded as a missed visit in the eCRF ("Not done"). The log line "If not done, specify reason" must be answered with the specific reason related to COVID-19, as above.

Description of visit scenarios

It is a requirement that all subjects attend the first 3 dosing visits (Visit 3, 4, 5) at the clinic according to protocol in order to ensure the 30 min. post-dose observation time for the 3 dosing visits. This will at the same time ensure proper training prior to home use. If attending the first 3 dosing visits is not possible, then the subject cannot take part in the trial.

Without compromising the safety of subjects and site personnel, it is expected that efforts are made to secure visit attendance at sites for visits Weeks 16, 56, 88, 104, 136, 152, 184, 216 and 248, in order to secure important efficacy assessments for the trial. Depending on national guidelines regarding COVID-19 and subject preferences, the remaining visits can follow 2 different scenarios as described below:

- 1) The subject is not restricted from attending visits at the clinic and continues to follow all procedures specified in the protocol.
- 2) Subject is not able to attend visits at the clinic, in which case the following procedure must be followed:
 - a. Site staff informs subject about the possibility of courier delivery of IMP and pregnancy test, if applicable.

- b. The subject verbally consents to providing contact details for shipping purposes and to receiving IMP at home (this needs to be documented in the subject's medical records).
- c. Site staff allocates IMP for the subject using the EDC system (RAVE®) as per protocol.
- d. Site staff sends the following items by a LEO-approved courier company:
 - i. Participant Information Sheet for home delivery.
 - ii. Log of Drug Administration.
 - iii. The appropriate amount of IMP.
 - iv. One sharps container, if required.
 - v. If required, sanitisers: alcohol wipes, cotton balls or gauze.
 - vi. For female subjects of child-bearing potential: one urine pregnancy test kit and Urine Pregnancy Test Instruction.
- e. Site staff contacts the subject (by telephone) and ensures the following:
 - i. The Participant Information Sheet has been read, is understood and agreed to.
 - ii. Subject is asked about concomitant medication use, concomitant procedures, adverse events, and pregnancy test outcome according to the original schedule of trial procedures.
- f. Site staff documents all the above in the subject's medical record at the clinic.
- g. Site staff enters all available information into the EDC system (RAVE®), see above Section "eCRF recording".

Home use of IMP

Injections of tralokinumab

Self-injection of tralokinumab is described in the protocol and does not change with this appendix.

Subjects who miss one or more doses need to have the missed doses documented in the eCRF with specific reason related to COVID-19 written in the comments log for each visit in scope.

Page 135 of 187

Further details on IMP-injection are provided in the Trial Product Handling Manual. Subjects will also receive a pamphlet with instructions for IMP home use and a Log of Drug Administration.

TCS

The use of TCS is described in the ECZTEND clinical trial protocol and does not change with this document.

Emollients

The use of emollients is described in the ECZTEND clinical trial protocol and does not change with this document.

Urine pregnancy test

The schedule of pregnancy testing does not change with this document. Subjects need to perform the urine pregnancy test kit at home if required per protocol. Urine pregnancy test kit is delivered by the site as per protocol. The subject will be provided with a Urine Pregnancy Test Instruction. Results should be communicated to the site by subject during telephone visit and documented in the eCRF and source documents.

Page 136 of 187

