To evaluate the efficacy of tralokinumab given as continuous treatment, re-treatment, or introduced for the first time in tralokinumab-naïve subjects	 IGA score of 0 (clear) or 1 (almost clear) at Weeks 16, 56, 88, 104, 136, 152, 184, 216, and 248 EASI75¹ at Weeks 16, 56, 88, 104, 136, 152, 184, 216, and 248
	Other endpoints
	 Change in EASI score from baseline² to Weeks 16, 56, 88, 104, 136, 152, 184, 216, and 248 Change in SCORAD from baseline² to Weeks 16, 56, 88, 104, 136, 152, 184, 216, and 248 Change in POEM score from baseline²³ to Weeks 16, 56, 80-88, 104, 128-136, 152, 184, 216, and 248 Change in DLQI/CDLQI⁴ score from baseline²³ to Weeks 16, 56, 80-88, 104, 128-136, 152, 184, 216, and 248 Change in EQ-5D-5L score from baseline²³, to Weeks 16, 56, 80-88, 104, 128-136, 152, 184, 216, and 248 Presence of anti-drug antibodies (yes/no) Time from first dose to permanent discontinuation of tralokinumab Proportion of time with EASI75¹ after first occurrence of EASI75 during treatment Proportion of time with IGA 0/1 after first occurrence of IGA 0/1 during treatment Worst Weekly Pruritus NRS at Weeks 16, 56, 88, 104, 136, 152, 184, 216, and 248 Eczema-related Weekly Sleep NRS at Weeks 16, 56, 88, 104, 136, 152, 184, 216, and 248 Use of topical treatment during the last week at Weeks 16, 56, 88, 104, 136, 152, 184, 216, and 248 Use of topical treatment during the last week at Weeks 16, 56, 88, 104, 136, 152, 184, 216, and 248

Page 48 of 187

- ¹ EASI75 and EASI50 calculated based on baseline EASI score in parent trial. Endpoint not applicable for subjects from the parent trial TRA-WEI-0015-I, as data from the parent trial will not be transferred to LEO Pharma.
- ² 'Change from baseline' defined as change from baseline in parent trial. Endpoints not applicable for subjects from the parent trial TRA-WEI-0015-I, as data from the parent trial will not be transferred to LEO Pharma.
- ³ Endpoint not applicable for subjects from the parent trial LP0162-1342, as these subjects will not have had POEM, DLQI/CDLQI, or EQ-5D-5L assessments in the parent trial, and thus are missing baseline assessments.
- ⁴ All subjects from the parent trial LP0162-1334, independent of the subject's age during participation in ECZTEND, will perform the Children's Dermatology Life Quality Index (CDLQI), an adolescent's pruritis NRS with a recall period of past 7 days, and an eczema-related sleep NRS with a recall period over the past 7 nights (see rationale in Section 12).

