7.1.3.4 Trial visits in the treatment period

Site visits until end of May 2021

Until end of May 2021, all subjects included in the trial prior to protocol version 10, attended site visits every 8 weeks. At each site visit, subject or subject's caregiver (or investigator) administered tralokinumab and assessed concomitant medications and treatment compliance. The following assessments were performed according to the trial procedures specified in Section 4.1:

- Efficacy assessments: IGA, EASI, and SCORAD.
- Safety assessments: weight, vital signs, physical examination, ECG, laboratory parameters (chemistry, haematology and immunoglobulin E), urinalysis, urine pregnancy test (if applicable), anti-drug antibodies (ADA), pharmacokinetics (PK), and AEs.
- Patient-reported outcomes: POEM, DLQI/CDLQI, EQ-5D-5L*, eczemarelated sleep NRS, worst weekly pruritus NRS/adolescent's pruritis NRS, and patient use of topical treatment.

• *The EQ-5D-5L is not performed by subjects from the parent trial

Details of assessments are described in Section 11.

LP0162-1334.

Visits after May 2021

After May 2021, subjects who re-consented to continue or consent to be included in the trial after May 2021, will attend 2 types of site visits (standard site visits and short site visits), interchanging with a telephone visit in between the site visits, according to the trial procedures presented in Section 4.2. The 3 types of visits are described below.

Standard site visit

At each standard site visit (Weeks 56, 88, 120, 152, 184, 216, and 248), subject or subject's caregiver (or investigator) will administer tralokinumab and assess concomitant medications and treatment compliance. In addition, the following assessments will be performed:

- Efficacy assessments: IGA, EASI, and SCORAD.
- Safety assessments: Weight, vital signs, physical examination, ECG, laboratory parameters (chemistry, haematology and immunoglobulin E), urine dipstick, urine pregnancy test (if applicable), ADA, PK, and AEs.
- Patient-reported outcomes: POEM, DLQI/CDLQI, EQ-5D-5L*, eczema-related sleep NRS, worst weekly pruritus NRS/adolescent's pruritis NRS, and patient use of topical treatment.
- *The EQ-5D-5L is not performed by subjects from the parent trial LP0162-1334.

Details of assessments are described in Section 11.

Short site visit

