At each short site visit (Weeks 40, 72, 104, 136, 168, 200, 232, and 264), subjects or subject's caregiver (or investigator) will administer tralokinumab and assess concomitant medications and treatment compliance. In addition, the following assessments will be performed:

- Efficacy assessments: IGA, EASI, and SCORAD.
- Safety assessments: Vital signs, physical examination, pregnancy test (if applicable), and AEs.
- Patient-reported outcomes: POEM, DLQI/CDLQI, EQ-5D-5L*, eczema-related sleep NRS, worst weekly pruritus NRS/adolescent's pruritis NRS, and patient use of topical treatment.

*The EQ-5D-5L is not performed by subjects from the parent trial

Details of assessments are described in Section 11.

LP0162-1334.

Telephone visit

Subjects will be contacted via telephone (telephone visit) 8 weeks after site visits (standard site visit or short site visit). For subjects from the parent trial LP0162-1334, this should as far as possible be a video call.

At each telephone visit, AEs, concomitant medication, treatment compliance, and pregnancy test result (if applicable) are assessed. The pregnancy test must be performed by the subject at home within 48 hours before the telephone visit, and a negative result informed to the site staff before the subject can continue treatment.

Delegation of the telephone visit to qualified personnel is allowed at the discretion of the investigator.

Details of assessments are described in Section 11.

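### Under the current schedule (Panel 5), the COVID-19 appendix leaves Week 120, alone among the standard site visits, off its list of visits to secure, so laboratory, ECG, ADA and PK data can be missing for 64 instead of 32 weeks

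*Protocol*

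**What the plan says.** Appendix 3K (description of visit scenarios) treats visits in three ways when COVID-19 restrictions apply.

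- The first dosing visits are compulsory on site: "It is a requirement that all subjects attend the first 3 dosing visits (Visit 3, 4, 5) at the clinic".
- For nine later weeks, sites are expected to see that "efforts are made to secure visit attendance at sites for visits Weeks 16, 56, 88, 104, 136, 152, 184, 216 and 248". The stated purpose is "in order to secure important efficacy assessments for the trial". The weeks are those of the secondary endpoints in Section 6, Panel 6: "IGA score of 0 (clear) or 1 (almost clear) at Weeks 16, 56, 88, 104, 136, 152, 184, 216, and 248".
- The remaining visits may be held by telephone when the subject cannot attend.

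At a converted visit the site records emollient use, AEs, concomitant medication and any pregnancy test result. For the rest the instruction is "All other assessments should be marked 'Not done' in the eCRF", apart from a few efficacy items and weight that are left blank. No later catch-up is described.

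Section 7.1.3.4 defines the two site visit types used after May 2021. The standard visits are listed thus: "At each standard site visit (Weeks 56, 88, 120, 152, 184, 216, and 248". Their content begins "Safety assessments: Weight, vital signs, physical examination, ECG, laboratory parameters (chemistry, haematology and immunoglobulin E), urine dipstick" and goes on to ADA and PK. Short visits (Weeks 40, 72, 104, 136, 168, 200, 232 and 264) have a smaller set: "Safety assessments: Vital signs, physical examination, pregnancy test (if applicable), and AEs". Panel 5 agrees with this text.

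**The concern.** The list was built from the efficacy endpoints, and the safety sampling schedule does not coincide with them. Two listed weeks (104 and 136) are visits at which no blood is drawn and no ECG recorded. The one week between them that has the full set (120) is not listed. A site that follows the appendix exactly can therefore secure every listed visit and still lose one complete set of safety samples.

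The primary objective is long-term safety, and Section 12 names ECG and clinical laboratory measurements among the methods for assessing it. The liver-enzyme withdrawal criteria in Section 10.2.2 can be applied only if blood is drawn. The SAP uses the same samples for shifts to the highest and lowest value, potentially clinically significant values and Hy's law (5.8.4), for ECG shift tables (5.8.5) and for ADA status (5.8.6). Appendix 3K gives no safety reason for leaving Week 120 out.

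**Working it through.** There is no sample size, power or error rate to reproduce. The check compares sets of weeks and takes differences.

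**Step 1. Compare the lists.**
- Secured weeks (Appendix 3K): 16, 56, 88, 104, 136, 152, 184, 216, 248.
- Panel 5 standard visits: 56 + 32k for k = 0 to 6, that is 56, 88, 120, 152, 184, 216, 248.
- Standard visits not secured: 120 only.
- Secured visits that are short visits: 104 and 136.

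**Step 2. Intervals under Panel 5.**
- Planned: 32 weeks between all consecutive standard visits.
- Week 120 by telephone, all secured weeks attended: 56, 88, 152, 184, 216, 248, with intervals of 32, 64, 32, 32 and 32 weeks. The affected one is 152 - 88 = 64, twice the plan.

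**Step 3. Subjects who changed schedule.** Panel 4 (until end of May 2021) has these assessments at Weeks 80, 104 and 128, and not at 88, 120 or 136. The documents give no distribution of entry dates, so the first-dose date is an assumption, shown as a range. A visit counts under Panel 4 if first dose + visit week falls on or before 31 May 2021, and under Panel 5 otherwise. Dates are nominal, since Section 7.1.3.3 allows some adjustment at the changeover.

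| First dose (assumed) | Last set before Week 152, with Week 120 by telephone | Gap to Week 152 (weeks) | Longest gap as planned (weeks) |
|---|---|---|---|
| to 17 Dec 2018 | Week 128 | 152 - 128 = 24 | 24 |
| 18 Dec 2018 to 11 Feb 2019 | Week 104 | 152 - 104 = 48 | 48 |
| 12 Feb to 3 Jun 2019 | Week 104 | 152 - 104 = 48 | 32 |
| 4 Jun to 23 Sep 2019 | Week 80 | 152 - 80 = 72 | 40 |
| from 24 Sep 2019 | Week 88 | 152 - 88 = 64 | 32 |

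In the first two rows Week 120 still fell under Panel 4, which plans none of these tests there, so converting it costs nothing. The omission lengthens the gap only for first doses from 12 Feb 2019. The first and fourth rows assume that Weeks 128 and 80, neither of them listed, were attended.

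**Step 4. Who can have the full 64 weeks.**
- LP0162-1334 subjects have a maximum of 114 weeks to EOT (Panel 5, footnote 2) and never reach Week 120.
- For a first dose on 24 Sep 2019, Week 152 is 23 Aug 2022. This is after the approximate US end date in Appendix 3J (May 2022). It is also after the German one (Aug 2021). There the EOT visit, which includes these tests, comes first.
- Taking month-end for the approximate country dates, Week 152 is reached for first doses up to about 3 Mar 2020 in Italy and Spain, 1 Jul 2020 in Canada and Japan, and 2 Jul 2021 in Poland.
- Protocol version 14.0 is dated 21-Feb-2022. A subject first dosed after 4 Nov 2019 reaches Week 120 after that date, so the point was still open when this version was issued.

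**The case against.** The strongest reply is that this is a deliberate pandemic trade-off. The list states its purpose and matches the endpoint weeks exactly, so it contradicts nothing. Week 120 is not freely convertible either: a subject who is not restricted follows the full protocol. Listing a week asks only for efforts, subject to the safety of subjects and staff, so someone who cannot travel would miss Week 120 anyway. Panel 5 also has an unscheduled-visit column with these tests, and SAP 5.8.4 includes unscheduled samples in its search for potentially clinically significant values. All of this is correct. It limits the expected gain and makes the gap conditional. It does not remove the point, because the unscheduled route is discretionary and nothing tells a site to use it after a converted Week 120.

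Four stronger readings are tempting, and the documents do not support them.

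- **That the appendix protects only efficacy.** Weeks 0, 2 and 4 are compulsory on site. Week 16 and six of the seven standard visits are on the list, and all of these carry the laboratory, ECG, ADA and PK tests.
- **That Week 120 is the only such visit between Weeks 88 and 152 for everyone.** This is true under Panel 5 only. Panel 4 has Weeks 104 and 128, and Week 104 is listed.
- **That the primary endpoint is compromised.** It is the number of AEs, and these must be collected whenever the subject is reached by telephone. Vital signs and physical examination continue at Weeks 104 and 136.
- **That the Panel 3 and 4 weeks and the patient-reported outcomes need the same repair.** That schedule ended in May 2021, so an edit now cannot change it. For the Week 80-88 and 128-136 endpoints, SAP 5.6.2 already takes the first existing value.

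**Conclusion.** The point holds for Panel 5 and Week 120. For a subject on Panel 5 by Week 88, the interval without laboratory, ECG, ADA and PK data doubles from 32 to 64 weeks. This rests on three conditions: Week 120 is converted to telephone, no unscheduled testing is done, and no EOT visit falls before Week 152. For subjects who changed schedule in May 2021 the nominal gap is 24, 48 or 72 weeks depending on entry date, and part of that was already planned. How many subjects meet the conditions is unknown, because the documents give neither entry dates nor conversion rates. The weakness is a modest and avoidable one in safety sampling. It should be corrected because long-term safety is the primary objective and the correction is small.

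**What to change.** Two changes to Appendix 3K.

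1. Reconcile the list of visits to be secured with the Panel 5 safety schedule, so that Week 120 is covered in the same way as the other standard site visits. If it is attended, the interval returns to 120 - 88 = 32 weeks.
2. State how laboratory, ECG, ADA and PK assessments missed at a converted visit are handled. One option is to take them at the next attended site visit through the existing unscheduled-visit column. For a converted Week 120 that would be Week 136, giving intervals of 136 - 88 = 48 and 152 - 136 = 16 weeks instead of one of 64. This matters more than the first change for subjects who cannot attend at all.

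The cost is about two sentences, with no new visit type, procedure or staff. The downside is one more visit for which attendance is encouraged during restrictions, and some samples taken later than planned. The existing condition on the safety of subjects and staff can stay as it is. No change is needed for Panels 3 and 4 or for the patient-reported outcome rule.
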